### 12.4 12-lead Electrocardiograms (ECGs)

The 12-lead ECG assessments will be performed during **Screening/Visit 1** (**ONLY** if more than two weeks since **EoS/Visit 2** of COL MIG-301 or COL MIG-302) and at visit **Month 1/Visit 2**, **Month 6/Visit 4**, and **Month 12/Visit 6/EoS/ET**. If **Screening/Visit 1** is the same day or within 2 weeks of **EoS/Visit 2** of COL MIG-301 or COL MIG-302 the data will be used for both parent and Gladiator studies. In that case the baseline for this data will be considered from parent study (301 or 302) where subject was randomized previously, and respective ECG parameters will be mapped by subject for new study for analysis. The question “When did the subject enter 305?” from CRF will be used to determine when the screening/Visit 1 for each subject was performed.

Shift tables describing abnormal shifts will be provided for ECG results, as appropriate by treatment group and dose, and will be classified as either:

- Normal
- Abnormal, Insignificant
- Abnormal, Significant

Worst value at any post baseline visit will be considered for the shift. Abnormal significant will be considered worse than Abnormal Insignificant and Abnormal Insignificant will be considered as worse than Normal.

Observed and change from baseline summaries will be presented for quantitative measurements using descriptive statistics.

The following ECG parameters will be summarized by each visit.

- Mean Heart rate
- PR interval, Aggregate
- QRS Duration, Aggregate
- QT Interval, Aggregate
- QTcB Interval, Aggregate
- QTcF Interval, Aggregate

Rhythm assessments will be presented in a listing.

QTcB is the QT interval corrected using Bazett’s formula. It will be calculated as:

$$QT \text{ (msec)} / (RR \text{ (sec)})^{1/2}$$

QTcF is the QT interval corrected using Fridericia’s formula. It will be calculated as:

$$QT \text{ (msec)} / (RR \text{ (sec)})^{1/3}$$

Categorical changes in ECG intervals will be summarized in frequencies and percentages based

on the categories as described in Appendix 16.4.

## 12.5 Physical Examination

If **EoS/Visit 2** of COL MIG-301 or COL MIG-302 is the same day as **Screening/Visit 1**, only a brief physical examination if indicated by an AE will be performed (as required by the earlier studies). In that case, the data will be used for both parent and Gladiator studies. The baseline for this data will be considered from parent study (301 or 302) where subject was randomized previously, and respective physical examination parameters will be mapped by subject for new study for analysis. The question “When did the subject enter 305?” from CRF will be used to determine when the screening/Visit 1 for each subject was performed.

If the subject is not enrolling in COL MIG-305 the same day they are completing COL MIG-301 or COL MIG-302, a complete physical examination will be performed during **Screening/Visit 1**. A complete physical examination of all body systems will include the following: general appearance, skin, HEENT, heart, lymph nodes, lungs, abdomen, extremities/joints, neurological systems, and mental status. At each visit, **Month 1/Visit 2, Month 3/Visit 3, Month 6/Visit 4, Month 9/Visit 5** and **Month 12/Visit 6/EoS/ET**, a brief symptom related physical examination will be performed if indicated by an AE. In this case, the baseline data will be used from current study for analysis.

Weight will be measured at **Screening/Visit 1**. BMI will be calculated by the database using the subject’s height recorded for COL MIG-301 or COL MIG-302 in specific parent study. Weight will also be measured at **Month 12/Visit 6/EoS/ET**.

The shift in physical examination evaluations will be summarized for each system for subjects who had a physical examination at each visit up to **EoS/Visit 6** as indicated by an adverse event.

- General appearance
- Skin
- Head, eyes, ears, nose, and throat (HEENT)
- Heart
- Lymph nodes
- Lungs
- Abdomen
- Extremities/joints
- Neurologic systems
- Mental status

For each system, the evaluation will be classified as:

- Normal

- Abnormal
- Not done

Worst value at any post baseline visit will be considered for the shift. Not Done will be considered worse than Abnormal and Abnormal will be considered as worse than Normal.

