- Time to headache relief and time to pain free after a second dose of lasmiditan for rescue or recurrence of migraine
- MBS free after a second dose of lasmiditan for rescue or recurrence of migraine
- Total number of migraine attacks and attacks treated with study medication over each 3 month

period

Resource utilization:

- Any CV events and/or related resource utilization such as visits to cardiologists, procedures, hospitalizations, new treatments or treatment adjustments for CV disease as collected in study COL MIG-301 or COL MIG-302 compared to on study **Visit 1** through **Visit 6/EoS/ET**.
- Any visits to an emergency room or physician's office for treatment of migraine as collected in study COL MIG-301 or COL MIG-302 compared to on study **Visit 1** through **Visit 6/EoS/ET** excluding study specific visits.
- Concomitant medications for the treatment of migraine and/or pain as collected in study COL MIG-301 or COL MIG-302 compared to concomitant medications for migraine and/or pain **Visit 1** through **Visit 6/EoS/ET**.
- Missed days of work and/or school or daily activities based on responses to MIDAS questionnaire.

Statistical Analysis:

Safety:

Adverse events will be summarized in terms of the proportion of patients and the proportion of attacks associated with any adverse event and with specific adverse events. Physical examinations, vital signs, clinical laboratory parameters (hematology, serum chemistry and urinalysis) and ECG parameters will be summarized in terms of change from baseline status at 1, 3, 6, 9 and 12 months or early termination.

Efficacy:

This is an open-label study with no control group. Efficacy data will be summarized using descriptive statistics. The proportion of attacks treated with study medication which respond at 2 hours will be calculated for each 3 month period.

Resource Utilization:

Resource utilization such as visits to cardiologists, procedures, hospitalizations, new treatments or treatment adjustments for CV disease as well as visits to the emergency room or a physician's office for the treatment of migraine will be summarized by treatment arm in terms of patient reported information recorded in study COL MIG-301 or COL MIG-302 compared to information reported at **Visits 2, 3, 4, 5, and EoS/ET/6**. Concomitant medication use for migraine and/or pain and missed days of work and/or school or daily activities based on responses to MIDAS questionnaire will be summarized by treatment arm.

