Treatment Period: Subjects will be asked to use lasmiditan as the first treatment for each new migraine attack within 4 hours of onset providing that the headache severity is at least moderate at that time and not improving. Subjects will record their response to the first dose over the next 48 hours using an electronic diary. For subjects randomized to lasmiditan 100 mg, if the migraine does respond within 2 hours (headache becomes pain free) but then recurs after 2 hours, a second dose of study drug may be taken up to 24 hours after the first dose. Subjects should not exceed a total dose of 200 mg of lasmiditan in a 24-hour period. Subjects will record their response to a second dose, taken for recurrence, for 48 hours in the electronic diary. The total time for recording response to study drug is up to 72 hours depending on whether or not a second dose of lasmiditan 100 mg is used. Subjects using an alternate medication other than a second dose of lasmiditan 100 mg for the treatment of migraine rescue or recurrence will report the use of medication and continue to record their responses in the electronic diary up to the 48 hour timepoint.

Subjects will be asked to return to the clinic at months 1, 3, 6, 9 and 12 (Visits 2, 3, 4, 5 and 6). At each visit a brief physical examination based on adverse events (AEs), vital signs and a urine pregnancy test on all WOCBP will be obtained. Blood and urine samples for clinical laboratory parameters (hematology, serum chemistry and urinalysis) will be obtained at **Month 1/Visit 2**, **Month 6/Visit 4** and **Month 12/Visit 6 (EoS/ET)**. A 12-lead ECG will be obtained at **Month 6/Visit 4** and **Month 12/Visit 6 (EoS/ET)**. C-SSRS will be completed at each visit. The MIDAS questionnaire will be completed at **Month 3/Visit 3**, **Month 6/Visit 4**, **Month 9/Visit 5** and **Month 12/Visit 6 (EoS/ET)**. At each visit, resource utilization, AEs, use of concomitant medication, use of study drug and patient diary compliance will be assessed; subjects who are

continuing will be dispensed study drug. Subjects who decide to withdraw at a scheduled visit should confirm the date of the visit is 7 days (± 2 days) from their last migraine treated with study drug. Subjects who decide to discontinue between scheduled visits are asked to contact the clinic to schedule an **ET /Visit 6** within two weeks (14 days) after discontinuation of dosing. The total time on study is up to 54 weeks (a maximum of 378 days).

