9.1.2 Physical Examination

If **EoS/Visit 2** of COL MIG-301 or COL MIG-302 is the same day as **Screening/Visit 1**, only a brief physical examination if indicated by an AE will be performed (as required by the earlier studies). If the subject is not enrolling in COL MIG-305 the same day they are completing COL MIG-301 or COL MIG-302, a complete physical examination will be performed during **Screening/Visit 1**. A complete physical examination of all body systems will include the following: general appearance, skin, HEENT, heart, lymph nodes, lungs, abdomen, extremities/joints, neurological systems, and mental status. At each visit, **Month 1/Visit 2, Month 3/Visit 3, Month 6/Visit 4, Month 9/Visit 5** and **Month 12/Visit 6/EoS/ET**, a brief symptom related physical examination will be performed if indicated by an AE.

Weight will be measured at **Screening/Visit 1**. BMI will be calculated by the database using the subject's height recorded for COL MIG-301 or COL MIG-302. Weight will also be measured at **Month 12/Visit 6/EoS/ET**.

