10.5.2 Physical Examinations, Vital Signs, ECG Parameters and Clinical Laboratory Test Values

By-subject listings of physical examinations, vital signs, ECG parameters and clinical laboratory data will include indications of values that are outside the reference ranges, and values that are clinically significant. Observed and change from baseline (Screening/Visit 1) values for vital signs, ECGs, and clinical laboratory test results will be summarized as appropriate by treatment arm and dose. Shift tables describing out-of-reference range shifts will be provided for vital signs, ECGs and clinical laboratory test results from the **Screening/Visit 1** to **EoS/Visit 6**, as appropriate by treatment arm and dose.

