## **12 SAFETY ANALYSIS**

This section details the specifications for summarizing safety endpoints.

Adverse event (AE) analyses will be presented on the Safety populations.

Laboratory, vitals, ECG, Physical examination and C-SSRS analyses will be presented on the Safety population.

Safety endpoints will be summarized using descriptive statistics.

Descriptive statistics for quantitative variables will include: n, mean, median, minimum, maximum, and standard deviation. Descriptive statistics for qualitative variables will include frequency counts and percentages. Adverse events will be summarized in terms of the proportion of subjects and the proportion of treated migraine attacks associated with any adverse event and with specific adverse events.

Values for all safety endpoints will also be presented in listings sorted by treatment group and subject.

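### SAP 12.5 ranks an examination that was not done as worse than an abnormal one, so a 'Not done' record can displace an abnormal finding in the physical examination shift table

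*SAP*

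**What the plan says.** SAP 12.5 grades each of ten body systems as Normal, Abnormal or Not done. For the shift from baseline it reduces all post-baseline visits to one grade: "Worst value at any post baseline visit will be considered for the shift". The ordering follows directly: "Not Done will be considered worse than Abnormal and Abnormal will be considered as worse than Normal". The table is to be "summarized for each system for subjects who had a physical examination at each visit up to" the end-of-study visit, as indicated by an adverse event. The SAP does not say whether this means an examination at every visit or at any visit.

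On when examinations take place, Protocol 9.1.2 says that at the post-baseline visits "a brief symptom related physical examination will be performed if indicated by an AE", and SAP 12.5 says the same. Protocol 5.4 is looser: "At each visit a brief physical examination based on adverse events (AEs), vital signs and a urine pregnancy test" are to be obtained.

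On reporting, the Statistical Analysis part of the Protocol Synopsis states that "Physical examinations, vital signs, clinical laboratory parameters (hematology, serum chemistry and urinalysis) and ECG parameters will be summarized" as change from baseline. Protocol 10.5.2 plans "By-subject listings of physical examinations, vital signs, ECG parameters and clinical laboratory data", but its change-from-baseline summaries and shift tables name only vital signs, ECGs and laboratory tests. SAP 12 adds that "Values for all safety endpoints will also be presented in listings sorted by treatment group and subject".

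**The concern.** 'Not done' means that nobody looked; it is not a degree of abnormality. Placing it at the top of a worst-case ranking lets an absent observation overwrite an observed one. A shift table exists to show how many subjects moved from normal to abnormal, and under this rule a subject who did so can be counted elsewhere. Normal results are overwritten in the same way. The 'Not done' cell then holds two kinds of subject: those never examined for that system after baseline, and those examined at least once but with a 'Not done' record at another visit.

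Physical examination is a listed safety endpoint (SAP 3.4), and this shift table is the only physical examination summary that SAP 12.5 specifies. SAP 5.6 carries the same tables from the May 2018 lock to the final lock, so the rule would be applied again.

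**Working it through.** The plan gives no figure on this point, so there is none to reproduce. The check applies the rule literally and then asks how far it could reach.

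**1. The rule as a maximum.** Code the SAP 12.5 ranking as Normal = 0, Abnormal = 1, Not done = 2, and take the maximum over post-baseline records for one body system.

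- {Abnormal, Not done}: max(1, 2) = 2, tabulated as 'Not done'.
- {Normal, Not done}: max(0, 2) = 2, tabulated as 'Not done'.
- {Abnormal} alone: 1, tabulated as 'Abnormal'.

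**2. Which patterns are affected.** There are five post-baseline visits (Months 1, 3, 6, 9 and 12). With n records there are 3^n − 2^n possible sequences containing at least one Abnormal. Of these, 2^n − 1 contain no 'Not done' and are tabulated correctly. The rest are displaced.

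| n records | Sequences with an Abnormal | Tabulated 'Not done' |
|---|---|---|
| 1 | 1 | 0 |
| 2 | 5 | 2 |
| 3 | 19 | 12 |
| 4 | 65 | 50 |
| 5 | 211 | 180 |

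These are counts of possible patterns, not expected frequencies. With the ranking changed to Abnormal above Normal, and 'Not done' lowest, the last column is 0 for every n.

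**3. The comparator.** The ECG shift in SAP 12.4 also takes the worst post-baseline value, but it orders only Normal, Abnormal Insignificant and Abnormal Significant. An ECG that was not performed has no rank, so it cannot displace a result. SAP 12.5 gives no reason for treating physical examinations differently.

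**4. Illustrative size.** Neither input below comes from the documents. Let k be the number of other post-baseline records for the system (0 to 4). Let q be the assumed chance that each is 'Not done', given that the examination showing the abnormality was done. If the other records are independent given that examination, the share of abnormal findings displaced is 1 − (1 − q)^k. For example, k = 2 and q = 0.2 gives 1 − 0.8² = 36%.

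| k | q = 0.05 | q = 0.2 | q = 0.5 | q = 0.8 |
|---|---|---|---|---|
| 0 | 0% | 0% | 0% | 0% |
| 1 | 5% | 20% | 50% | 80% |
| 2 | 9.8% | 36% | 75% | 96% |
| 3 | 14.3% | 48.8% | 87.5% | 99.2% |
| 4 | 18.5% | 59.0% | 93.8% | 99.8% |

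**5. What decides k and q.** If a visit without an adverse-event-driven examination leaves no record, k is often 0 and nothing is lost. If such a visit is stored as 'Not done', k and q are both high. Separately, a brief examination aimed at one symptom may leave other systems unexamined, and these may be stored as 'Not done'. The documents settle none of this. Restricting the table to subjects examined at every visit would not prevent displacement, because 'Not done' is scored per system.

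**The case against.** The strongest case against is about reach and consequence, since the wording and logic are not in dispute.

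- **The trigger is not shown.** Displacement needs two post-baseline records for the same system in the same subject, one Abnormal and one 'Not done'. The CRF and dataset specifications are not among the documents. This stands: the rule's effect is certain but its frequency is unknown.
- **The contrast between Protocol 5.4 and 9.1.2 is weak.** Protocol 5.4 itself ties the examination to adverse events, and the visit-by-visit text in 5.5 consistently makes it conditional on one. On the natural reading, visits without an event have no examination. This makes the high cells of the grid less likely. It does not help with systems skipped within an examination that did take place.
- **The grid excludes nothing.** It runs from 0% to 99.8% on assumed inputs. Independence is also doubtful, because a system found abnormal may be more likely to be re-examined. This stands; the grid only shows what the frequency depends on.
- **The protocol's support is mixed.** The Synopsis asks for a change-from-baseline summary, but Protocol 10.5.2 asks only for listings of physical examinations. That is true, but once the SAP commits to a shift table, the table should classify correctly.
- **'Not done' stays a separate category.** This is correct, so the defect is one of precedence. The content of that category is still mixed.
- **The safety consequence is small.** Post-baseline examinations follow adverse events that are reported in their own right, and the listings keep every grade. This stands, and it sets the severity.

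**Conclusion.** The concern holds, at minor severity. As written, SAP 12.5 tabulates a body system with one abnormal and one 'Not done' post-baseline record as 'Not done', and no other section corrects this. That conclusion rests on the text alone and is held with high confidence.

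The size cannot be stated. It ranges from no displacement, when a system has a single post-baseline record, to most abnormal findings, if unexamined visits are routinely stored as 'Not done'. The effect is confined to one descriptive table: no primary or secondary endpoint, test or analysis population uses this ranking.

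**What to change.** Amend SAP 12.5 as follows:

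1. Derive the worst post-baseline grade from examined results only, with Abnormal worse than Normal.
2. Show 'Not done' as a separate count, used only when a system has no post-baseline evaluation.
3. State who is in the table. Subjects with at least one post-baseline examination is the workable definition; if examination at every visit is intended, the SAP should say so.
4. State whether a visit without an examination, or a system left out of a brief one, creates a 'Not done' record.

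The cost is two or three sentences and a small change to one table program. No new data are needed.

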### **12.6 Columbia-Suicide Severity Rating Scale (C-SSRS)**

The C-SSRS will be used to assess suicidal ideation and behavior. Listings will present all C-SSRS data for subjects with at least one positive response to any C-SSRS question at any time during the study.

If **Screening/Visit 1** is the same day or within 2 weeks of **EoS/Visit 2** of COL MIG-301 or COL MIG-302 the data obtained will be used for both studies. The baseline for this data will be considered from parent study (301 or 302) where subject was randomized previously, and respective C-SSRS parameters will be mapped by subject for new study for analysis. The question “When did the subject enter 305?” from CRF will be used to determine when the screening/Visit 1 for each subject was performed.

The “since last visit” version of questionnaire will be administered at **Screening/Visit 1 (ONLY** if more than two weeks since **EoS/Visit 2** of COL MIG-301 or COL MIG-302) and at visit **Month 1/Visit 2, Month 3/Visit 3, Month 6/Visit 4, Month 9/Visit 5** and **Month 12/Visit 6/ EoS/ET**. In this case, the baseline data will be used from current study for analysis.

### **12.7 Cardiovascular Medication Use**

A summary of baseline cardiovascular medication use (e.g. anti-anginal, anti-hypertensive, anti-arrhythmic, etc.) will be provided for the safety population. In addition, a summary of patients with changes to cardiovascular medication use post-baseline, including initiation of a new cardiovascular medication and an increase in dose in current cardiovascular medications, will be provided for the safety population.

## **13 RESOURCE UTILIZATION**

A summary table will present counts and percentages of subjects who visited a cardiologist, or having procedures, hospitalizations, new treatments, or adjustments to treatments for any cardiovascular conditions or disease since the parent study. Counts and percentages of subjects with emergency room or urgent care visits for migraines since parent study will be presented. Data on CV related events at different visits as **Month 1/Visit 2, Month 3/Visit 3, Month 6/Visit 4, Month 9/Visit 5** and **Month 12/Visit 6/ EoS/ET** will be also presented for subjects in frequencies and percentages. This data will include different providers (cardiologist, primary care, emergency room, other), hospitalizations, performed procedures and changes in cardiovascular medications in last 6 months. This summary will be presented on the Safety population by treatment groups.

Additional information regarding these visits or changes will be presented in a listing.

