9.1.1.3 Resource Utilization

During **Screening/Visit 1** subject information reported during participation in Phase 3 study COL MIG-301 or COL MIG-302 about any CV events and/or related resource utilization such as visits to cardiologists, procedures, hospitalizations, new treatments or treatment adjustments for CV disease will be reviewed and updated as appropriate. In addition the previously reported information regarding any ER visits or visit to physician's office for migraine treatment will be reviewed and updated. The information recorded for COL MIG-301 or COL MIG-302 will be carried over into the database for the COL MIG-305. At each visit, **Month 1/Visit 2, Month 3/Visit 3, Month 6/Visit 4, Month 9/Visit 5** and **Month 12/Visit 6/EoS/ET** the subject will again be asked about resource utilization during their time on study.

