10.8 Resource Utilization

By-subject listings of any resource utilization will be listed and will be summarized using descriptive statistics, separated by treatment arm and visit. Days missed from work and/or school or daily activities will be tabulated from information recorded on the MIDAS scale separated by treatment arm and visit.

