**3.5 Resource utilization:**

- Any CV events and/or related resource utilization such as visits to cardiologists, procedures, hospitalizations, new treatments or treatment adjustments for CV disease on study **Visit 1** through **Visit 6/EoS/ET**.
- Any visits to an emergency room or physician’s office for treatment of migraine on study **Visit 1** through **Visit 6/EoS/ET** excluding study specific visits.
- Concomitant medications for the treatment of migraine and/or pain **Visit 1** through **Visit 6/EoS/ET**.
- Missed days of work and/or school or daily activities based on responses to MIDAS questionnaire.
- MIDAS Total score.

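### SAP 13 tabulates emergency room or urgent care visits for migraine, but the endpoint in the Protocol and SAP 3.5 is emergency room or physician's office visits, and the change is not declared

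*SAP*

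**What the plan says.** The Protocol synopsis, under resource utilization, gives the endpoint as "Any visits to an emergency room or physician's office for treatment of migraine as collected in study COL MIG-301 or COL MIG-302", to be compared with the same information on study from Visit 1 to the final visit, with study-specific visits left out. Its statistical paragraph repeats the two visit types: "visits to the emergency room or a physician's office for the treatment of migraine will be summarized by treatment arm".

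Protocol 9.1.1.3 describes collection. At Screening/Visit 1, "previously reported information regarding any ER visits or visit to physician's office for migraine treatment will be reviewed and updated". At later visits the subject is asked again about resource utilization, without the visit types being restated. Protocol 10.8 gives the analysis in general terms: "By-subject listings of any resource utilization will be listed and will be summarized using descriptive statistics, separated by treatment arm and visit".

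SAP 3.5 keeps the Protocol's two visit types, "Any visits to an emergency room or physician’s office for treatment of migraine on study", and also leaves out study-specific visits.

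SAP 13 specifies the tables. Its one sentence on migraine visits is "Counts and percentages of subjects with emergency room or urgent care visits for migraines since parent study will be presented". The rest of the section concerns cardiovascular care. The by-visit breakdown, which has a provider list including primary care, opens with "Data on CV related events at different visits as". A closing line promises a listing with further detail on the visits and changes already mentioned.

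**The concern.** The SAP defines an endpoint in one section and tabulates a different set of visits in another. Tables are programmed from the analysis section, so the version in SAP 13 is the one likely to be reported under the endpoint's name.

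Protocol 5.3 makes patient-reported resource use for migraine episodes, set against COL MIG-301 or COL MIG-302, an additional objective. The Protocol describes the parent-study information as covering emergency room and physician's office visits. An on-study figure built from emergency room and urgent care visits is a different quantity. Anyone who sets the two side by side, as the objective invites, would be comparing unlike things without being told. The study is open-label with no control group, so the parent-study information is the main context for such a figure.

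**Working it through.** The plan gives no figure to reproduce. The check is a comparison of categories, followed by what can be said about size.

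**Step 1: categories side by side.**

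| Place | Emergency room | Physician's office | Urgent care | Study-specific visits left out |
|---|---|---|---|---|
| Protocol synopsis, endpoint | yes | yes | not named | yes |
| Protocol synopsis, analysis | yes | yes | not named | not restated |
| Protocol 9.1.1.3, Visit 1 review | yes | yes | not named | not stated |
| SAP 3.5, endpoint | yes | yes | not named | yes |
| SAP 13, migraine table | yes | not named | yes | not restated |

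Only SAP 13 departs on visit type. It does so in both directions: one component lost, one gained.

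**Step 2: does another part of the SAP bring office visits back?**

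- Primary care in SAP 13 belongs to the data introduced by "Data on CV related events at different visits as". It describes providers seen for cardiovascular reasons, not for migraine.
- The closing listing in SAP 13 covers visits already mentioned there. Office visits for migraine are not among them, and a listing is not a summary by arm.
- SAP 8.2 covers MIDAS scores, headache days and average pain, not health-care visits.

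**Step 3: is the change declared?** The opening of Protocol Section 10 requires changes to the analysis methods, with their justification, to be described in the SAP. SAP 5.1 records changes to analysis populations, mild headaches, the missing-data sensitivity analysis, subgroups and associated symptoms. Nothing there concerns resource utilization.

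**Step 4: what happens to the count?** SAP 13 counts subjects, not visits. Let E, O and U be the sets of subjects with at least one emergency room, physician's office or urgent care visit for migraine.

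- Endpoint count = |E ∪ O| = |E| + |O not in E|
- SAP 13 count = |E ∪ U| = |E| + |U not in E|
- Difference (SAP 13 minus endpoint) = |U not in E| − |O not in E|

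Subjects with both an office and an urgent care visit but no emergency room visit appear in both terms and cancel. That leaves:

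Difference = (urgent care only) − (office only)

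The documents give neither number. The difference may be negative, zero or positive. Even at zero, the subjects counted would not be the ones the endpoint describes.

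**The case against.** The strongest reply is that this is a matter of terms with no demonstrated loss. Protocol 10.8 still calls for all resource utilization to be listed and summarized, and SAP 13 does not withdraw that. SAP 13 never says that emergency room and urgent care visits are the only ones to be shown. The CRF is not among the documents, so urgent care might be the CRF's label for unscheduled office visits. The endpoint is one part of an additional, descriptive objective in a safety study whose sample size rests on no statistical hypothesis.

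Much of this stands. The data are not shown to be lost; what is lost is a component of the one table specified for this endpoint. The CRF coding cannot be checked. Protocol 9.1.1.3 names office visits only for the Visit 1 review, and the Schedule of Assessments refers loosely to specialists, emergency rooms and the like, so separate capture of office visits at every later visit is plausible but not established. None of this makes the SAP 13 table agree with SAP 3.5. If urgent care is a CRF label with a wider meaning, the SAP has to say so.

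A reader might also infer a large false reduction in migraine care: if office visits were 50% to 80% of all migraine visits, the reported figure would seem to fall by that much against the parent studies. The documents do not support this, for four reasons.

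- They give no such share.
- SAP 13 counts subjects, so someone with both an office and an emergency room visit is still counted.
- Adding urgent care offsets some or all of any loss.
- SAP 13 specifies no parent-study column or before-and-after contrast in which a reduction would appear. How the parent studies tabulated these visits, and over what period, is not given.

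**Conclusion.** The inconsistency is real. The SAP's migraine-visit table does not measure the SAP's own endpoint, it departs from the Protocol in the same way, and the departure is not declared where the Protocol requires it. The on-study figure would also not be like-for-like with the parent-study information in the Protocol objective.

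The size cannot be derived. It is the number of subjects with urgent care visits only minus the number with office visits only, and both are unknown. The conclusion rests on reading SAP 13 as the complete specification of the migraine-visit output, which fits the text because no other SAP section specifies one. It does not rest on any assumption about how often patients use each kind of care. It also does not show that office-visit data will be missing from the database or from the study report.

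No primary or secondary endpoint, analysis population, error rate or power is touched. This is a modest point, worth correcting because it is clear and cheap to put right.

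**What to change.** Rewrite the migraine sentence in SAP 13 so that it matches SAP 3.5. Present counts and percentages of subjects with at least one emergency room or physician's office visit for migraine, leaving out study-specific visits, by treatment arm and by visit as Protocol 10.8 requires. Give one row per visit type and a total that uses the SAP 3.5 definition. If urgent care is collected, show it as a separate row outside that total.

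Before doing so, check the CRF. If it does not capture office visits for migraine separately after Visit 1, or records them under another label, state this in SAP 13 and record and justify the change in SAP 5.1. SAP 3.5 should then carry the definition actually used.

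The cost is one rewritten sentence and a few table rows, with no new data collection if the item is captured. If it is not, the cost is a short entry in SAP 5.1. SAP 5.6 plans the same tables for the May 2018 and final locks, so a table already produced to the present wording would need a rerun or an explanatory note.
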